The secondary objective is to compare the primary and secondary outcomes when stratified by stone size. This will allow us to explore the efficiency between Moses and thulium laser on treating large vs. small stones. Previous literature suggested that stone size was associated with operative time.^{ix} Patients will be separated based on the size of their stones: 3-10 mm or 11-20 mm and then randomized to holmium laser with Moses or thulium laser. Patients will be randomized into the groups by a ratio of 1:1.

Research Design and Methods

This study will be a randomized trial comparing ureteroscopy with laser lithotripsy with the Lumenis® Pulse™ P120H holmium laser system with the Moses technology (holmium laser with moses) versus the Soltive™ SuperPulsed Laser System with the thulium fiber laser technology (thulium laser). The primary objective is to compare the procedural time (minutes). We will keep strict timing from the minute the ureteroscope is inserted into the patient to the time the ureteroscope has been removed. The following information will be collected as secondary outcomes: (1) stone free rate; (2) total operative time (minutes); (3) fragmentation/dusting time (minutes, total time to fragment the stone, including the laser was in use and time of pedal pauses); (4) lasing time (minutes, time the laser was in use, not including pedal pauses); (5) total energy used (kilojoules, kJ); (6) laser efficiency (mm per minute); (7) number of times the laser pedals are pressed (left, right, and total pedal presses); (8) stone analysis; (9) complications; (10) quality of life survey (WISQOL short form) both pre-operatively and post-operatively and (11) physician evaluation of the laser. Physicians will complete a one page survey at the end of the case evaluating the laser (survey included as attachment). A total of 3 clinic visits (i.e., pre-operative visit, the stone surgery, and one post-operative visit) will be needed for this study. Stone parameters (i.e. size, location, Hounsfield units, presence of hydronephrosis, stone volume), demographic information, co-morbidities, and post-operative parameters will be collected from the medical record.

Number of Participants

NCT04963062
Protocol 2021-0695

Approximately 164 patients will be enrolled (see Data Analysis for sample size justification).

Inclusion Criteria

1. Patients at least 18 years of age, and less than 89 years old.

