2. Patients with renal or ureteral urinary stones who require endoscopic treatment in the outpatient operating room
3. Patients' stone size in a single renal unit of 3-10 mm and 11-20 mm. Stone size is defined as the largest diameter of a single stone on pre-operative CT. Patients with multiple stones will be included as long as their largest stone size falls within the above parameters.

Exclusion Criteria

1. Patients under 18 years of age and over 89 years old.
2. Pregnant patients
3. Patients with transplant kidneys
4. Patients with irreversible coagulopathy
5. Patients with known ureteral stricture disease
6. Patient who do not have a pre-operative CT.
7. Non-English speaking, vulnerable patients such as lacking of decision-making capability, prisoner, adult unable to consent, will not be enrolled.

Recruitment methods

Patients who are to be scheduled for laser lithotripsy treatment of urinary stones as outpatients will be approached for study participation. During patients' pre-operative clinic visit, eligibility screening (by reviewing patients' medical record that is relevant for inclusion/exclusion criteria) will occur before recruitment. If patients meet the inclusion criteria, they will be initially approached by a study team member who also works in the urology clinic (i.e., the surgeon informs the patient that there's a research study they may be eligible for, and asked if they want to learn more about it).

No other recruitment materials will be used in this study. Holmium laser with Moses or thulium laser to treat stones is our routine care. Patients have been informed about the laser lithotripsy treatment before they schedule their surgery. We will only recruit patients from the outpatient OR, so this will not include patients who come in emergently through the Emergency Department.

NCT04963062
Protocol 2021-0695

No compensation will be provided to participants.

Consent Process

A study team member who is affiliated with the patient's clinical care (e.g., the surgeon) will initially approach the patients who are scheduled for laser lithotripsy treatment of urinary stones. (i.e., informed that there's a research study they may be eligible for, and asked if they want to learn more about it).

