6. Patients will undergo stone surgeries with the laser that they are randomized to. A 200 micron fiber will be used with both machines. The patient's stone(s) will be treated in accordance with our routine clinical practice of fragmenting stone into small pieces (≤ 2 mm). One stone fragment will be collected for stone analysis if the patient does not already have a stone analysis on file (this is also standard of care). The faculty surgeons will perform all surgeries. We are unable to blind the surgeon to the laser used as the laser fibers and laser machines appear and sound different.
7. Procedural time as well as other information (see study design for the detail information) is collected.
8. After surgery, the patients will all have at least an abdominal x-ray within 1 month of surgery, if a CT scan has not already been completed(this is the standard of care). They will also be asked to fill out a WISQOL short form at their one-month follow up appointment. Otherwise, they will continue on our normal postoperative pathway. Postoperative complications will be collected.

Comparison of usual care and study procedures

Compared with our routine care, the only interventions imposed on subjects as a result of this study are (1) pre-procedural randomization to laser lithotripsy with either holmium laser with Moses or thulium laser, and (2) the use of patient & surgery information collected in describing our results. All the other activities are part of our routine clinical practice.

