Since we have 5 surgeons participating in this study, we will use university-based cloud service (such as OneDrive) to temporarily save the enrollment log. Study team member will use their Net ID to access the enrollment log. The enrollment log is completely deidentified. Only participant ID (such as 101, 102) and the laser each participant is randomized to are saved in the enrollment log. Once we complete data collection, we will permanently delete it from the cloud.

Share of results

NCT04963062
Protocol 2021-0695

Some of the information collected for this study will go in the patient's medical record. This includes the results of the one-month post-operative image, stone analysis, stone surgery, and all clinic visits information as these are being conducted as standard of care. All other information from research specific procedures will NOT go in the patient's medical records.

We only publish aggregated results. No individual results will be shared. We will not share the data with outside institutions.

Economic burden to participants

This study does not place financial burden to patients. The study interventions are our routine clinical practice to treat stones. It will be same as they are not involved in this study.

The cost of the two laser treatments are equivalent.

Data Analysis

The data collected will be analyzed as an intention-to-treat analysis. Statistical analyses will include T-test and, if appropriate, Chi-square tests (e.g., for categorical data), and two-way MANOVA. Patient demographics and stone characteristics will be summarized as appropriate as continuous variables (mean and standard deviation) or categorical variables (frequency, percentage). To compare the two groups, continuous variables such as procedural time, total OR time, WISQOL etc., will be analyzed using T test and two-way MANCOVA (stratified by stone size 3 - 10 mm or 11-20 mm). The surgeon will be controlled as a covariate. Categorical variables such as stone free rate will be analyzed using chi-square.

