We plan to enroll 164 patients in this study. Patients will be stratified into two groups according to their stone size (3-10 mm or 11-20 mm) and then randomized to either holmium laser with Moses or thulium laser. The stone size is defined as the largest stone size (largest diameter on pre-operative CT), if patients have multiple stones. Previous literature suggested stone size is associated with operative time.^{ix} A significance level of 0.05 will be used with a two-sided two-sample equal-variance t-test. Group sample sizes of 33 and 33 achieve 80% power to detect a significant difference between the means when the mean difference is 4.6 minutes with a standard deviation of 6.5 minutes. We also decide to increase the sample size by 25% (41 patients per group). This will allow for the possibility that the randomization scheme is intra-operatively abandoned for some reason (e.g., equipment failure), that the planned procedure was unable to be completed for some reason, as determined by the surgeon in

charge of the case, and/or that the patient – after his/her procedure – wishes to withdraw from the study and exclude his/her information from our analysis.

ⁱ Scales CD Jr, Smith AC, Hanley JM, Saigal CS; Urologic Diseases in America Project. Prevalence of kidney stones in the United States. *Eur Urol*. 2012 Jul;62(1):160-5.

ⁱⁱ Geraghty RM, Jones P, Somani BK. Worldwide Trends of Urinary Stone Disease Treatment Over the Last Two Decades: A Systematic Review. *J Endourol* 2017 Jun;31(6):547-556.

ⁱⁱⁱ Assimos D, Krambeck A, Miller NL, et al: Surgical Management of Stones: American Urological Association/Endourological Society Guideline, PART II. *J. Urol.* 2016.

^{iv} Andreeva V, Vinarov A, Yaroslavsky I, et al. Preclinical comparison of superpulse thulium fiber laser and a holmium:YAG laser for lithotripsy. *World J Urol*. 2020 Feb;38(2):497-503.

^v Ventimiglia E, Doizi S, Kovalenko A, et al. Effect of temporal pulse shape on urinary stone phantom retropulsion rate and ablation efficiency using holmium:YAG and super-pulse thulium fibre lasers. *BJU Int*. 2020 Jul;126(1):159-167.

^{vi} Bagrodia A, Gupta A, Raman JD, et al. Predictors of cost and clinical outcomes of percutaneous nephrolithotomy. *J Urol*. 2009 Aug;182(2):586-90.

^{vii} Schuster TG, Hollenbeck BK, Faerber GJ, Wolf JS Jr. Complications of ureteroscopy: analysis of predictive factors. *J Urol*. 2001 Aug;166(2):538-40.

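### Procedural time includes the work on every stone treated, but no measure of total stone burden enters its analysis, so precision is given up that the required pre-operative CT could supply

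*Protocol*

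**What the plan says.** - **Endpoint.** Protocol, Research Design and Methods, times the procedure from ureteroscope insertion to removal. Study Procedures, step 6, shows that one or more stones may be treated in that window: "The patient's stone(s) will be treated in accordance with our routine clinical practice".
- **Entry.** Inclusion Criteria, item 3, defines size by the largest single stone on the pre-operative CT and adds: "Patients with multiple stones will be included as long as their largest stone size falls within the above parameters". It sets no ceiling on the number of stones or their total volume.
- **Stratum.** The sample-size text under Data Analysis also uses the largest stone. Study Procedures, step 5, instead has the total stone size calculated and split into the two bands.
- **Data collected.** Research Design and Methods lists "Stone parameters (i.e. size, location, Hounsfield units, presence of hydronephrosis, stone volume" among the items taken from the medical record. It does not say whether volume is summed over all stones, and stone count is not listed.
- **Analysis.** Protocol, Data Analysis, gives a t-test and a two-way MANCOVA by size band, and states: "The surgeon will be controlled as a covariate". The SAP's Data Analysis Plan assigns procedural time to a Wilcoxon test with no covariate or stratum, and uses stone volume only as a baseline descriptor.

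**The concern.** The protocol stratifies because earlier literature linked stone size to operative time. A two-band split of one diameter captures that link only coarsely. The time needed plausibly depends on how much stone has to be fragmented, and this varies widely between patients in the same band. Variation in burden that is left out of the primary analysis stays in the residual error. The estimated laser difference is then less precise than it need be, and a chance imbalance in burden between the lasers goes uncorrected. At stake is the width of the interval around the laser effect, in a trial planned around a difference of 4.6 minutes.

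**Working it through.** **Inputs from Protocol, Data Analysis**
- Test: "A significance level of 0.05 will be used with a two-sided two-sample equal-variance t-test".
- Planned size: "Group sample sizes of 33 and 33 achieve 80% power to detect a significant difference between the means".
- Effect and spread: a difference of 4.6 min and an SD of 6.5 min.
- Inflation: "We also decide to increase the sample size by 25% (41 patients per group"; 164 in total.

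**Assumed input.** R² is the share of procedural-time variance, left after band and surgeon, that log total stone volume explains. The documents give no value. I use 0.10 to 0.40, and take the stated 6.5 min as the within-band SD.

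**Step 1: the plan's own figure.** With 33 per group the noncentrality is 4.6 / (6.5 × √(2/33)) = 2.87 on 64 degrees of freedom, which gives power of 80.8%. The stated 33 reproduces. Then 33 × 1.25 = 41.25, taken as 41, and 4 × 41 = 164 (two lasers by two bands). That is 41 per laser within a band and 82 per laser overall.

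**Step 2: spread of burden within a band.** For single spherical stones volume scales with diameter cubed:
- 3-10 mm: (10/3)³ = 37.0
- 11-20 mm: (20/11)³ = 6.0

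These figures hold under either stratum definition, because largest and total coincide for a single stone. Multiple stones add spread under both. By largest stone, each further stone adds volume without changing the band. By summed diameters (one reading of total), two 5 mm stones count as 10 mm but hold 2 × 5³/10³ = 0.25 of the volume of one 10 mm stone.

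**Step 3: gain from adjustment.** Interval width is multiplied by √(1 − R²), and the effective sample by 1/(1 − R²).
- R² = 0.10: width × 0.949 (about 5% narrower); sample × 1.11
- R² = 0.40: width × 0.775 (about 23% narrower); sample × 1.67

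**Step 4: chance shift from imbalance in burden.** The 95% range is ±1.96 × √(2/n) × √R² × 6.5.

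| n per laser | √(2/n) | R² = 0.10 | R² = 0.40 |
|---|---|---|---|
| 41 (within band) | 0.221 | ±0.9 min | ±1.8 min |
| 82 (overall) | 0.156 | ±0.6 min | ±1.3 min |

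**Step 5: steps 3 and 4 describe one cost.** At 41 per laser the unadjusted 95% half-width is 1.96 × 6.5 × 0.221 = 2.81 min. With R² = 0.40 the adjusted half-width is 2.81 × 0.775 = 2.18 min, and 2.18² + 1.78² = 7.9 = 2.81². The shift in step 4 is the part of the interval that adjustment removes, not a further loss.

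**Step 6: validity.** In simulations at 33 per laser (4,000 runs per scenario; correlations of 0.3, 0.5 and 0.7 between burden and time), the type I error was between 4.6% and 5.3% with and without adjustment.

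**The case against.** The case against has five parts.

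1. **The stratum may not rest on the largest stone.** A reader might infer that one 9 mm stone and four 9 mm stones always share a stratum. The documents do not settle this. Under Study Procedures, step 5, if total means summed diameters, four 9 mm stones come to 36 mm, outside both bands. This stands. The loss of precision does not depend on it, because the spread in step 2 exists under either definition.
2. **Randomisation already protects the comparison.** This stands in full. A reader might infer bias or an inflated false-positive rate; neither follows.
3. **Power may be ample.** The Study Objectives make the overall laser comparison primary and the comparison by size band secondary. On the stated 4.6 and 6.5 min, power is about 99% at 82 per laser and 89% at 41. A reader might infer that the trial is underpowered. That would follow only if the 6.5 min came from simpler cases. With burden correlations of 0.3 to 0.7, the SD would then be 6.8 to 9.1 min, and power at 33 per group 77% to 53%. The documents do not say where the 6.5 min comes from, so this remains a possibility only.
4. **The gain is assumed.** No document supports a particular R², and stratification already takes up part of the size effect. This stands. At the low end the interval narrows by only about 5%.
5. **The data may not be ready.** A volume summed over all stones is not promised, so some new measurement may be needed. The SAP also lists ablation speed and ablation efficiency, and the protocol lists laser efficiency, but these are separate outcomes and do not adjust procedural time.

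**Conclusion.** The point holds as a matter of precision. The endpoint reflects all stones treated, and no burden measure enters its analysis in either document. Volume is collected and described, so the gap lies in the primary analysis rather than in a complete failure to use it.

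The expected gain is a 5-23% narrower interval, on the assumed R² of 0.10-0.40 after band and surgeon, with 6.5 min as the within-band SD and R² carried over to the minutes scale. It would be tempting to say that imbalance could move the result by several minutes. On these assumptions the 95% limit stays below 2 min even within a band, and that shift is already counted in the interval width. This is a recommended, inexpensive improvement, not a threat to validity. The conflicting stratum definitions are a separate matter and need correcting in any case.

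**What to change.** 1. Confirm that recorded stone volume is the total over all stones to be treated, measured on the required pre-operative CT before surgery. Record the stone count as well.
2. Prespecify the primary analysis of procedural time as ANCOVA with laser, stone-size band as used in the randomisation, surgeon and log total stone volume. If times are skewed, use log time, with the rule for choosing the scale fixed before any comparison by laser. Report the effect in minutes as well, so that it can be read against the planned 4.6 min.
3. Keep the SAP's Wilcoxon test as a sensitivity analysis. This also settles which of the protocol's and SAP's differing methods is primary.
4. Reconcile the stratum definition in Study Procedures, step 5, with Inclusion Criteria, item 3, and Data Analysis. The definitions can disagree: stones of 8 and 6 mm fall in the lower band by largest stone and in the upper band by summed diameter (14 mm).

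The cost is SAP and protocol wording, some CT measurement time for patients with several stones, and an effect on a ratio scale if log time is used. No extra scan, visit or patient is needed.

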If the patient is interested in the study, a member of the research team will approach him/her for enrollment. Consent process will be conducted face to face. Participants will be provided a written consent form in person. No waiting time is expected between informing the prospective participant and obtaining the consent.

Consent will take place during patients' pre-operative clinic visit. If patients are interested and there is not enough time to consent the patient in urology clinic, study information will be sent home with the patient and the patient will then be consented before their surgery in a private room (pre-operative room). Pre-operative room provides 1-1 1/2 hours of time. This should be ample time to conduct the consent process before surgery anesthesia.

All information about the study will be provided, and ample time will be made available for the participants to consider participation in the study.

Patient Randomization

Patients will be randomized (ratio 1:1) at the time of enrollment to be treated with either the holmium laser with Moses or the thulium laser. We will use Permuted Block Randomization (stratified by stone size 3 - 10 mm or 11-20 mm) (block size 4).

Study Procedures

1. The study team members review patients' medical record during patients' pre-operative clinic visit to see whether patients meet inclusion/exclusion criteria.
2. If patients meet the inclusion criteria, a study team member who is affiliated with the patient's clinical care (e.g., the surgeon) will initially approach the patients who are scheduled for laser lithotripsy treatment of urinary stones. (i.e., informed that there's a research study they may be eligible for, and asked if they want to learn more about it).
3. If the patient is interested in the study, a member of the research team will approach him/her for enrollment.
4. Patients will be asked to fill out a WISQOL short form at their pre-operative visit. This is standard of care for all stone patients in clinic.

5. Patients' total stone size (pre-operative CT) will be calculated and divided into two groups. Those with stones 3-10 mm and those with stones 11-20 mm. They will then be randomized to either the holmium laser with Moses or the thulium laser (randomization ratio 1:1) group.

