Holmium laser with Moses and thulium lasers will be used for this study. Both are FDA approved lasers for the treatment of urinary calculi through an endoscope. The holmium laser with Moses emits two separate laser pulses with a short time interval between them. The first pulse divides the water between the laser fiber tip and the stone and the second pulse hits the stone unobstructed.^{xi} The goal is to increase stone ablative volume and decrease retropulsion of the stone. The thulium laser has a different wavelength than the holmium laser with Moses and thus has slightly different energy properties. It has also been shown to increase ablative volume and decrease retropulsion without any safety concerns.^{xii} The holmium laser with moses is currently the most common laser used at our institution for treatment of urinary stones. The thulium laser has been used at our institution on a trial basis previously and will be available soon for use on a daily basis for surgical cases at our institution. There is no learning curve associated with the thulium laser. The two lasers have similar specifications; the two fibers are the same size and will interact with the instruments (ureteroscopes) similarly.

Study Timelines

For each patient, the study duration is from consent to the one-month post-operative clinic visit. Patients will be on study for approximately 6-8 weeks.

Risks and Potential Benefits

Treatment with the holmium laser with Moses and thulium laser can be associated with the common risks of hematuria, stent pain, passing fragments, UTI, dysuria. The rare risks include perforation of the urinary tract, bleeding, and stricture of the ureters. However, the surgeon who will perform the surgery will not exceed safe levels. All procedures performed by surgeons who are board-certified. If significant injury or inefficient fragmentation of the stone occurs, the surgeon will have the discretion to transition to a different laser for patient safety reasons. All patients enrolled will undergo routine post-operative follow up including clinic appointments and imaging evaluation. Any complications will be recorded, reported, and treated appropriately.

There is a risk that your information could become known to someone not involved in this study, which might make you uncomfortable.

There is no direct benefit. Potentially, more efficient laser may be identified which may result in faster procedural time and lower complication rates.

Safety Monitoring Plan

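### Patients consented in clinic are randomised about 2-4 weeks before surgery, so cancelled operations lose randomised patients and no-stone ureteroscopies dilute the laser difference, with no rule for either

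*Protocol*

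**What the plan says.** Protocol, Patient Randomization, ties allocation to enrolment: "Patients will be randomized (ratio 1:1) at the time of enrollment to be treated with either the holmium laser with Moses". Consent Process gives two routes. The usual one is the clinic: "Consent will take place during patients' pre-operative clinic visit". If time runs out there, "the patient will then be consented before their surgery in a private room (pre-operative room".

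Study Timelines defines time on study, "the study duration is from consent to the one-month post-operative clinic visit", and gives its length: "Patients will be on study for approximately 6-8 weeks". The wait between consent and surgery is not stated.

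Research Design and Methods defines the primary outcome, procedural time, as the interval from ureteroscope insertion to removal. Lasing time is a separate secondary outcome. Study Procedures step 6 says that surgeons cannot be blinded. The data management section describes a shared enrolment log that shows the assigned laser against each participant number.

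On analysis, Data Analysis says: "The data collected will be analyzed as an intention-to-treat analysis". The sample-size text adds 25% for randomisation abandoned during surgery, procedures that could not be completed, and withdrawal after the procedure. Neither that text nor the SAP's Data Analysis Plan says what happens to a randomised patient who has no ureteroscopy, or whose ureteroscopy finds nothing to treat.

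**The concern.** Renal and ureteral stones from 3 mm are eligible, and size is fixed on a pre-operative CT. Between a clinic allocation and the operation, a stone may pass or the operation may be cancelled. Two different problems follow.

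- **No operation.** The patient is in the intention-to-treat population but has no primary outcome. If loss is unrelated to arm, the cost is sample size. If the known assignment influences who is cancelled or rescheduled, the arms are no longer comparable, and extra patients do not repair that.
- **Ureteroscopy with no stone found.** The scope-in to scope-out time is recorded and looks valid, but neither laser contributed to it. Such values pull the arm means together and, if they are short, widen the spread.

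The primary objective is time to acceptable fragmentation with each laser. With no rule in place, whether such patients count would be settled after the allocation is known.

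**Working it through.** **Length of the wait (derived).** Time on study is 6-8 weeks, of which about 4 weeks follow surgery: 6 - 4 = 2 and 8 - 4 = 4, so about 2-4 weeks. This applies only to patients consented in clinic; the documents do not give their share.

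**The plan's own figure.** Inputs from Protocol, Data Analysis: difference 4.6 min, SD 6.5 min, two-sided alpha 0.05, equal-variance t-test, 33 per group. The noncentrality is 4.6 / (6.5 × √(2/33)) = 2.87 on 64 degrees of freedom, giving power 80.8%. At 32 per group it is 79.6%, so 33 reproduces. Then 33 × 1.25 = 41.25, stated as 41. Since 4 × 41 = 164, I read 41 as the number per laser within each size stratum, which makes 2 × 41 = 82 per laser overall. With no losses, power is 88.6% at 41 per group and 99.5% at 82 per laser, taking 4.6 and 6.5 min to apply to both comparisons.

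**Case 1: missing procedures.** The expected difference stays at 4.6 min if loss is unrelated to arm; only n falls (rounded down).

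| Share lost (assumed) | n per group in a stratum | Power |
|---|---|---|
| 5% | 38 | 86.1% |
| 10% | 36 | 84.2% |
| 15% | 34 | 82.0% |
| 19.5% (8/41) | 33 | 80.8% |
| 25% | 30 | 76.9% |

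At 82 per laser, power is still 96.3% with 30% lost (57 left). The allowance therefore covers up to 19.5% missing, although its listed reasons do not name loss before surgery.

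**Case 2: a time is recorded but no stone is found.** Let a fraction f in each arm have times D minutes shorter with no laser effect. Then difference = 4.6 × (1 - f) and SD ≈ √(6.5² + f(1 - f)D²). Both f and D are assumptions.

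| f | D (min) | Difference (min) | SD (min) | Power, 41 per group | Power, 82 per laser |
|---|---|---|---|---|---|
| 0 | - | 4.60 | 6.50 | 88.6% | 99.5% |
| 5% | 10 | 4.37 | 6.86 | 81.4% | 98.2% |
| 5% | 20 | 4.37 | 7.83 | 70.5% | 94.5% |
| 10% | 10 | 4.14 | 7.16 | 73.5% | 95.7% |
| 10% | 20 | 4.14 | 8.85 | 55.3% | 84.6% |

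For example, at f = 10% and D = 20: 4.6 × 0.9 = 4.14, and √(42.25 + 0.09 × 400) = √78.25 = 8.85. If those times are no shorter (D = 0), power at 41 per group is 85.3% for f = 5% and 81.3% for f = 10%.

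**Arm-related loss.** The documents give nothing from which to size this.

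**The case against.** A reader might infer that every patient lost in the wait dilutes the primary comparison. The documents do not support that. The outcome is scope time, so a patient who is never operated on has a missing value, which lowers n but leaves the 4.6 min difference alone. Only a ureteroscopy with nothing to lase dilutes.

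A reader might also compute the power loss from 33 per group, which gives 72-61% at f = 5% and 64-47% at f = 10%. Those figures treat the whole allowance as already spent. The plan enrols 41 per group, and the primary objective compares the lasers overall, where power stays at about 85% or above in every scenario tabulated.

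Other objections have weight. The rates and time gaps are assumed, and one f is applied to all patients although renal stones and stones up to 20 mm are also eligible. The SAP names a Wilcoxon test for procedural time, so the t-test figures do not carry over exactly. The allowance for procedures that could not be completed may be meant to include no-stone cases. If so, that judgement rests with an unblinded surgeon, and the text does not say how it fits with intention to treat. Finally, nothing in the protocol suggests that operations would be rescheduled by arm: both lasers are described as routine care at equivalent cost, and the shared log is de-identified. Arm-related loss is therefore an open possibility, not a demonstrated bias.

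What stands is the sequence. For patients consented in clinic, an unconcealed allocation precedes events that decide whether there is an outcome at all, and no rule covers them.

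**Conclusion.** The point holds as an avoidable design weakness, not a fatal one. Early allocation exposes the trial to lost patients and possible arm-related loss before surgery. No-stone ureteroscopies add dilution. On the assumed 5-10% and 10-20 minutes, power falls from 89% to about 81-55% within a size stratum, and from 99.5% to about 98-85% overall. The by-size comparison, a stated secondary objective, carries most of that cost. These figures rest on the inferred split of 164 into four groups of 41, the plan's difference and SD, and rates that the documents do not supply. They do not show that the overall primary comparison is underpowered. The possible bias cannot be quantified and is the better reason to act, because the sample-size allowance does not address it.

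**What to change.** Keep consent, eligibility and the size stratum at the clinic visit. Amend Patient Randomization and Study Procedures step 5 so that the assignment is drawn on the day of surgery, in the pre-operative area or operating room, before the ureteroscope is inserted. Patients cancelled before that day are then never randomised.

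The draw should not wait until a stone has been seen. The procedural-time clock would already be running, so allocation and laser set-up would fall inside the primary outcome, possibly by different amounts in the two arms.

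A draw before insertion still leaves some cases where no stone is found. Data Analysis and the SAP should state how these enter the primary analysis, with the same handling in both arms, and should require their number to be reported by arm.

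The cost is a protocol amendment and having both lasers available for each study case. Day-of-surgery consent already implies allocation that day for some patients. The protocol also foresees a change of machine during a case ("the surgeon will have the discretion to transition to a different laser for patient safety reasons"), though that does not show that both are reserved for every case. No extra patients or procedures are needed.
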